1.2.3.2 GLP Toxicology and Safety Studies

Single Dose Oral Toxicity Study in Dogs (GLP)

A GLP study was performed to evaluate the toxicity and toxicokinetics of ONC201 following a single oral dose to Beagle dogs followed by a 2-day or an 18-day recovery period. Dogs received a single dose of 0, 4.2, 42, or 120 mg/kg by oral gavage. There was no mortality observed in this study. There were no definitive ONC201-related effects on group mean body weight or body weight gain, EKG rhythm or morphology, mean heart rate or arterial blood pressure, urinalysis, hematology parameters, coagulation parameters, clinical chemistry parameters, erythrocyte morphology, gross findings on necropsy, changes in absolute or organ to body or organ to brain weights.

Although not statistically significant, there were some dose-related decreases in group mean food consumption for the first week following dosing. The 120 mg/kg females had statistically significantly decreased group mean food consumption compared to the vehicle control group on Days 14, 15 and 18. There were no clinical signs of toxicity noted following a single dose of 4.2 mg/kg ONC201. At a dose of 42 mg/kg and 120 mg/kg, some dogs had clinical observations at approximately 1 hour post-dose including decreased activity, emesis, salivation, and/or soft, loose or mucous feces. Of uncertain relationship to ONC201 administration was the unusual finding of mononuclear cell inflammation in the blood vessels of the brain, which was multifocal and mild in one high dose female at Day 3, multifocal and minimal in one high dose female at Day 19, and minimal and focal in one control female at Day 19. Similar findings were not noted in any male animal.

Based on the results of this study, the NOAEL following oral administration of ONC201 at single doses of 4.2, 42 or 120 mg/kg to Beagle dogs is considered to be at least 42 mg/kg.

CONFIDENTIAL

Single Dose Oral Toxicity and Toxicokinetic Study in Rats with a 19-Day Recovery and a 30-Minute Intravenous Infusion Toxicokinetic Arm (GLP)

A GLP study was performed to evaluate the toxicity of ONC201 following a single oral dose in Sprague-Dawley rats with necropsy after a 2-day or an 18-day recovery period. Rats received 0, 12.5, 125, or 225 mg/kg ONC201 by oral gavage.

There was no mortality observed in this study. There were no definitive ONC201-related effects on coagulation parameters, clinical chemistry parameters, gross findings at necropsy. There were no clinical signs of toxicity noted at single doses up to 225 mg/kg ONC201. There were no ONC201-related statistically significant changes in hematology parameters or clinical chemistries outside of the historical control range for these values.

At a dose of 225 mg/kg, clinical signs of toxicity were limited on the day of dose administration to one out of twenty males and one out of twenty females that showed signs of decreased activity and abnormal gait and stance. The male was also noted to have increased respiration. All were normal by Day 2. No ONC201 related changes were noted during the functional observational battery (CNS activity) performed on Day 1 between 1 and 2 hr post-dose with the exception of one 225 mg/kg female noted as having decreased activity. A statistically significant decrease in group mean body weight gain was noted on Day 7 for the 225 mg/kg males. A statistically significant decrease in group mean food consumption was noted on Day 7 for the 225 mg/kg males.

On Day 3 the 225 mg/kg females also had increased glucose, cholesterol, sodium and chloride. Sodium and chloride were statistically significantly increased for the 225 mg/kg females. Only cholesterol and chloride were outside historical control ranges for this laboratory on day 19. As the increase in cholesterol was only noted for the females and no corresponding liver findings were observed, the significance of this finding is unknown. Though within normal historical control values for these laboratories, chloride remained increased for the 225 mg/kg males while cholesterol remained increased for the 225 mg/kg females.

Changes in brain and liver weights were noted but did not occur in a dose-dependent manner and no microscopic changes were noted for in these organs for the high dose females. These changes were considered incidental and unrelated to treatment. At the Day 3 necropsy, ONC201-related minimal to mild edema and/or mixed cell inflammation was present in the non-glandular stomach of 225 mg/kg males and females. This edema and inflammation was primarily submucosal, although in some animals the inflammation involved the serosa or mesentery. Two males and one female had minimal focal ulceration of the overlying squamous epithelium. Similar stomach findings were seen in 125 mg/kg animals, with a lower incidence than in 225 mg/kg. There was complete resolution of all stomach lesions at the Day 19 necropsy, indicating full recovery.

Based on the results of this study, the NOAEL following oral administration of ONC201 at single doses of 12.5, 125 or 225 mg/kg to Sprague-Dawley rats is considered to be at least 125 mg/kg.

Evaluation of the Effect of ONC201 Dihydrochloride on Respiratory Function Following Single-Dose Administration in Rats (GLP)

A GLP study was performed to determine the potential effects of ONC201 dihydrochloride on respiratory function in rats following a single oral gavage administration. Twenty four (6/group) male rats received 0, 12.5, 125, or 225 mg/kg ONC201 by oral gavage and were monitored in plethysmographic chambers. The oral administration of ONC201 dihydrochloride at 12.5 and 125 mg/kg did not induce any biologically relevant effects on respiratory rate, tidal volume or minute volume in conscious male rats. A marginal to moderate transient decrease in respiratory rate and minute volume was observed following the oral administration of ONC201 dihydrochloride at 225 mg/kg, which resolved by 2 hours.

1.2.4 Pharmacokinetic Studies

1.2.4.1 Pharmacokinetic Studies in Animals

The measured half-life of ONC201 in mice is ~6 hours with intravenous administration as measured by an HPLC-UV assay. In rats, exposure to ONC201 was dose-dependent and approximately dose-proportional. Exposure to ONC201 was slightly greater in female rats after a single oral gavage dose. Plasma $t_{1/2}$ ranged from 2.3 to 8.4 hours in 7 of 8 profiles. Clearance ranged from 7.5 to 23.5 L/hr/kg in 7 of 8 profiles. Volume of distribution ranged from ~49 to ~103 L/kg in 6 of 8 profiles.

In dogs, exposure to ONC201 following oral gavage dosing at 4.2, 42, and 120 mg/kg ONC201 was dose-dependent and increased with greater ONC201 dose levels (Figure 1.6). Exposure to ONC201 was similar in male and female dogs with the observation that all mean male C_{max} and AUC values were slightly greater than those corresponding female values. Elimination of ONC201 from plasma was similar between the mid and high dose levels; mean $t_{1/2}$ ranged from 4.6 to 7.8 hours. Mean $t_{1/2}$ following the low dose of 4.2 mg/kg was ~1 hour [the half-life determined for dogs in the low dose group may represent more of a distribution phase half-life rather than the terminal plasma elimination half-life]. Overall elimination of ONC201 was greater following the low dose.

[figure not shown]

Figure 1.6 Dog Plasma Concentrations (Mean ± SD) of ONC201 Plotted as a Function of Time Following a Single Oral Gavage Dose to Male and Female Beagle Dogs.

1.2.4.2 Pharmacokinetic Studies in Humans

In a Phase I dose escalation clinical trial of ONC201 in advanced solid tumors, the pharmacokinetics of single agent ONC201 was determined by LC-MS-MS analysis of plasma collected in the first cycle of therapy within 21 days of drug administration (Fig 1.7; Table 1.1). Trends of increasing exposure with dose were consistent with dose proportionality. Patients receiving 625mg ONC201 exhibited a mean half-life of 11.3 hours and achieved a Cmax of 3.6 ug/mL (~9.3 uM), which occurred at 1.8 hours following administration (Tmax). The mean volume of distribution was 369 L, consistent with a large distributive volume.

Mean AUC was 37.7 h. μ g/mL and mean CL/F was 25.2 L/h. Generally, CL/F was observed to be variable but consistent across all dose groups. There were no apparent relationships between drug CL/F and patient sex and age. Noticeable, shallow trends were observed with patient weight and BSA. An overall increase in CL/F was observed as weight and BSA increased. Although a slight upward trend was observed, there was no strong correlation between CL/F and CLCR.

Stronger correlations were observed with the distributive volume estimate and patient weight and BSA. A increase in volume of distribution was observed with increasing patient weight or BSA, as expected. Trends of decreasing exposure with increasing weight were observed in plots of Cmax/Dose and AUC/Dose versus patient weight. Weight normalized CL/F was plotted versus Dose, showing a similar trend to un-normalized CL/F.

[figure not shown]

Figure 1.7: Mean ONC201 plasma concentrations versus time following the first dose of ONC201. Concentrations are shown as (A) A mean for each dose cohort, or (B) for individuals treated at 625 mg.

Table ONC201	C_{max} (ug/mL)	T_{max} (h)	T_{lag} (h)	AUC_{last} (h.ug/mL)	λ_Z (h ⁻¹)	t_{1/2} (h)	AUC (h.ng/mL)	V_{Z/F} (L)	CL/F (L/h)	1.1
Mean	3.6	1.8	0.02	37.0	0.076	11.3	37.7	369	25.19	
SD	2.6	0.9	0.08	41.6	0.046	5.2	41.6	193	14.22	

pharmacokinetic parameters determined in patients receiving 625 mg ONC201 (n=24).

1.3 Clinical Studies

The clinical safety of ONC201 has been evaluated in a phase I clinical trial. The design was an open-label, dose-escalation phase I trial of monoagent ONC201 in patients with advanced, refractory tumors who had exhausted or refused standard treatment options for their respective indications. The primary objective of this study was to determine the recommended phase 2 dose (RP2D) of ONC201 administered orally in patients with advanced cancers, as well as to evaluate the safety and tolerability of the drug. Secondary objectives included pharmacokinetics

CONFIDENTIAL

and pharmacodynamics evaluation of ONC201 and preliminary assessment of anti-tumor efficacy.

An accelerated dose escalation design was employed to reduce the number of patients treated at potentially sub-therapeutic dose and to accelerate the determination of the recommended phase 2 dose. Ten evaluable patients (aged 47-80 years) received oral ONC201 once every 3 weeks at five dose levels ranging from 125 to 625 mg. The study design included only one patient per cohort until any patient experiences a grade 2 adverse event during the first cycle of treatment, defined as 21 days. Five dose levels (125 mg, 250 mg, 375 mg, 500 mg, 625 mg) were selected for the study. Enrollment at each subsequent dose level required that all patients enrolled at the prior dose level completed Cycle 1 dosing and were evaluated 21 days later to assess safety.

On average, patients received 2.9 doses of ONC201. Nine out of ten patients completed at least 2 cycles, 4 patients completed at least four cycles, and one patient received six cycles and remains on therapy. 625 mg was the highest dose administered and was determined to be the RP2D. Dyspnea and fatigue was observed in a few patients, which was attributed to their underlying disease. No drug-related toxicities Grade >1 were observed in any patients in this study.

Another arm of this study has been opened to evaluate weekly dosing. Three patients have been treated with 375mg ONC201 on a weekly basis and six patients have been treated with 625mg on a weekly basis. As of September 8, 2016, there have been no reports of drug-related adverse events in any of these patients. All three 375mg and six of the 625mg patients have successfully completed the DLT window (21 days). Based on these findings, the recommended administration schedule of ONC201 is 625mg once every week.

Additional clinical studies of ONC201 are enrolling, including a Phase I clinical trial in advanced solid tumors and multiple myeloma, a Phase I/II clinical trial in relapsed/refractory acute leukemias and high-risk myelodysplastic syndrome (MDS), a Phase I/II clinical trial in relapsed/refractory Non-Hodgkin's lymphoma (NHL) and a Phase II clinical trial in bevacizumab-naïve glioblastoma multiforme (GBM).

1.4 Rationale

ONC201 is a first-in-class small molecule with consistent antitumor activity in difficult-to-treat cancers as demonstrated using *in vitro*, *ex vivo*, and *in vivo* models. The mechanism of action of ONC201 appears to involve the activation of the integrated stress response (ISR) that causes a downstream inactivation Akt and ERK signaling as well as induction of the pro-apoptotic TRAIL pathway. Multiple myeloma is highly sensitive to ER stress-inducing agents that trigger the ISR such as proteasome inhibitors used to treat multiple myeloma. The efficacy of ONC201 has been demonstrated in numerous solid and liquid tumor cell lines and patient sample that are refractory to chemotherapy and targeted therapies, including bortezomib refractory multiple myeloma. ONC201 is effective in tumor cells harboring diverse mutations in genes such as p53, KRAS, Raf, EGFR and others that render resistance to chemotherapy and targeted therapies. Multiple myeloma have been selected for evaluation in this trial based on preclinical efficacy as well as the mechanism of action of ONC201 that involves engagement of the ISR, inactivation of Ras signaling, and induction of the TRAIL pathway that should be effective in these tumors based on preclinical and clinical evidence. Administration of ONC201 with dexamethasone in this study is based on preclinical evidence that ONC201 synergizes with dexamethasone in multiple myeloma cell lines (Figure 1.8).

[figure not shown]

Figure 1.8 ONC201 synergizes with dexamethasone in multiple myeloma. Combination indices (left) and exemplary combination results (right) for cell viability of RPMI-8226 cells treated with ONC201 and/or dexamethasone (72 hrs, n=2).

ONC201 will be administered once every week. This infrequent dosing schedule was selected based on the preclinical findings that these schedules are effective and well tolerated in mouse models. This observation is rationalized by the sustained intratumoral activity of the molecule for several days to weeks following a single dose of the drug.

In preclinical studies, ONC201 acute toxicity is transient and generally resolves within several hours of administration. Preclinical data with ONC201 suggests saturation of efficacy at a human equivalent of 125mg. A dose of 625 mg is expected to exceed the dose (and associated Cmax) with maximal efficacy by 5-fold and thus higher doses may not be explored.

The frequency of once a week dosing is being evaluated based on the excellent clinical safety and PK observations in the first-in-human study.

2 OBJECTIVES AND ENDPOINTS

2.1 Objectives

2.1.1 Primary Objective

- Determine the antitumor efficacy of ONC201 in combination with dexamethasone.

2.1.2 Secondary Objectives

- Evaluate the overall safety profile of ONC201 in combination with dexamethasone.
- Assess the pharmacodynamic (PD) effects of ONC201 in combination with dexamethasone.
- Assess effect of ONC201 in combination with dexamethasone on survival endpoints.

2.2 Endpoints

2.2.1 Primary Endpoint

- Overall response rate (ORR) using the International Myeloma Working Group response criteria.

2.2.2 Secondary Endpoints

- Overall safety profile of ONC201 as characterized by type, frequency, severity, timing and relationship to study therapy of adverse events and laboratory abnormalities.
- Effects of ONC201 on pharmacodynamic (PD) markers.
- Effects of ONC201 on survival endpoints (i.e., progression-free survival, time to progression, and duration of response)

3 STUDY DESIGN

3.1 Overview

This is a Phase 1/2, open-label study of ONC201 in combination with dexamethasone in adult patients with relapsed/refractory multiple myeloma. This trial intends to explore the antitumor efficacy of orally administered ONC201 at 625 mg weekly in patients receiving concomitant dexamethasone, using the International Myeloma Working Group response criteria.

Throughout the study, AEs, SAEs, laboratory values, vital signs, physical examination findings, ECOG performance status, and EKGs will be obtained. Toxicity will be evaluated according to National Cancer Institute Common Terminology Criteria for Adverse Events (NCI CTCAE), version 4.03. Study drug may be discontinued if a patient experiences study treatment-related toxicity.

Serial blood samples to measure relevant biomarkers will be collected at prespecified time points as indicated in Section 7.

3.2 Number of Patients

Phase 1 is expected to enroll up to 12 patients and Phase 2 will enroll up to 30 evaluable patients over the course of 2 years. The actual sample size will depend on the clinical results.

3.3 Dose and Planned Scheme

In Phase I, ONC201 is intended to be administered once every week at 375mg or 625mg. Dexamethasone will be administered same day of each ONC201 administration. One cycle is defined as 21 days (three weeks), which is also the dose-limiting toxicity (DLT) window.

Phase 1 of the study involves a 3 + 3 dose escalation with a starting dose of 375mg ONC201 followed by an escalation to 625mg ONC201. This will allow assessment of the safety, tolerability, pharmacodynamic effects, and efficacy of two doses of weekly ONC201 in combination with dexamethasone. Dexamethasone will be administered at 20mg weekly. In the unexpected event that >1/6 patients in the first cohort experience a DLT, dose de-escalation will proceed by a 3 + 3 design using 8mg dexamethasone and 375mg ONC201. Further dose de-escalation would involve step-wise decreasing 125mg increments of ONC201. Dose de-escalation below 125mg ONC201 and 8 mg dexamethasone will not be permitted.

Once a recommended phase 2 dose (RP2D) has been determined in Phase I based on a favorable benefit/risk ratio (anticipated to be 625mg ONC201 with 20mg dexamethasone), the study will progress to Phase 2 of the study.

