- Assess effect of ONC201 in combination with dexamethasone on survival endpoints.

Primary Endpoint

- Overall response rate (ORR) using the International Myeloma Working Group response criteria.

Secondary Endpoints

- Overall safety profile of ONC201 as characterized by type, frequency, severity, timing and relationship to study therapy of adverse events and laboratory abnormalities.
- Effects of ONC201 on pharmacodynamic (PD) markers.
- Effects of ONC201 on survival endpoints (i.e., progression-free survival, time to progression, and duration of response).

Study design

This is a Phase 1/2 open-label study of ONC201 administered orally once every week in combination with dexamethasone to patients with relapsed/refractory multiple myeloma.

In Phase 1 of the study, patients will receive 625 mg ONC201 once every week in combination with dexamethasone using a 3+3 dose escalation design that will evaluate up to 625mg ONC201 weekly with 20mg dexamethasone. Three weeks is defined as a treatment cycle.

Phase 1 of the study will involve a safety cohort of at least 6 relapsed/refractory multiple myeloma patients who will receive ONC201 and dexamethasone.

In Phase 2 of the study, patients will receive 625mg ONC201 once every week. Dexamethasone will be administered at a dose determined in Phase 1. Patients may not cross over from Phase 1. Tumor assessments will be conducted using the International Myeloma Working Group response criteria. The study plans to enroll 42 patients over a period of 2 years.

Eligibility criteria

Inclusion

1. Patients must be refractory to, or not a candidate for, established therapy known to provide clinical benefit for their malignancy.
2. Measurable disease M protein component in serum (at least 0.5 g/dL) and/or urine (if present) (≥ 0.2 g excreted in a 24 hour collection sample), or serum free light chain level ≥ 10 mg/dL, provided the serum free light chain ratio was abnormal.
3. Able to swallow and retain oral medication.
4. All previous therapies for cancer, including radiotherapy, major surgery and investigational therapies discontinued for ≥ 14 days (≥ 28 days for mitomycin C or nitrosoureas) before study entry, and all acute effects of any prior therapy resolved to baseline severity or Grade ≤ 1 Common Terminology Criteria for Adverse Events (CTCAE v4.03), except alopecia or parameters defined in this eligibility list.
5. Age ≥ 18 years.
6. ECOG performance status ≤ 1 .

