5.2 ONC201 Administration

Patients will receive 625 mg of ONC201 on an outpatient basis. The study drug, ONC201, will be supplied in capsule form for oral dosing. Patients should take designated capsules of ONC201 at approximately the same time on each day of drug administration. Patients will be instructed to not eat for 2 hours pre and 2 hours post dosing. If the patient vomits after taking ONC201, they should not retake the dose. Missed doses will not be made up.

ONC201 should be taken with a glass of water and consumed over as short a time as possible. Patients should swallow the capsules as a whole and not chew them. Do not crush or empty the capsule. If vomiting occurs during the course of treatment, no re-dosing of the patient is allowed before the next scheduled dose. The occurrence and frequency of any vomiting during a treatment cycle must be noted as an adverse event. In addition, on the days of drug administration the exact time of any episodes of vomiting within the first 4 hours post-dosing on that day must be noted whenever possible.

Dexamethasone will be obtained and administered per standard of care guidelines for multiple myeloma patients. Administration of dexamethasone is recommended approximately 6 hours (+ 2 hours) after ONC201.

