7 STUDY PROCEDURES

Note that hematology, blood chemistry, and urinalysis, below, refers to any biologic sampling done for safety or efficacy testing, as detailed in the Schedule of Activities. For example, patients with multiple myeloma may undergo a 24-hour urine collection but this is not explicitly defined in the text below. The Schedule of Activities take precedence over text in this section.

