7.3 Treatment

ONC201 will be orally administered at 625mg weekly day 1, day 8, and day 15 of each treatment cycle (21 days). Dexamethasone will be administered at the indicated dose on each day that ONC201 is administered in each treatment cycle (day 1, day 8, and day 15). Administration of dexamethasone is recommended approximately 6 hours (+ 2 hours) after ONC201.

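### The ONC201 dose rules disagree: Section 3.3 starts Phase 1 at 375 mg, Sections 5.2 and 7.3 give 625 mg without limiting it to a phase or cohort, and both steps of Table 6.1 lower ONC201 only from 625 mg

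*Combined protocol and SAP*

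**What the plan says.** **Starting dose.** Section 3.3 is the only section that sets out cohort doses. It describes "a 3 + 3 dose escalation with a starting dose of 375mg ONC201 followed by an escalation to 625mg ONC201", with dexamethasone at 20 mg weekly, and carries the RP2D into Phase 2. The anticipated RP2D is 625 mg with 20 mg. Elsewhere the dose is given differently:

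- Section 5.2: "Patients will receive 625 mg of ONC201 on an outpatient basis".
- Section 7.3: "ONC201 will be orally administered at 625mg weekly day 1, day 8, and day 15 of each treatment cycle (21 days".
- Synopsis, Phase 1: patients "will receive 625 mg ONC201 once every week in combination with dexamethasone using a 3+3 dose escalation design that will evaluate up to 625mg".
- Synopsis, Phase 2: "In Phase 2 of the study, patients will receive 625mg ONC201 once every week".

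Section 7 has a precedence rule: "The Schedule of Activities take precedence over text in this section".

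**Dose modification.** For Grade 3 or 4 events Table 6.1 names fixed doses at which to resume: 500 mg ONC201 with 8 mg dexamethasone after the first instance, and 375 mg with 8 mg after the second. Section 5.5 withdraws any patient with a drug-related Grade 4 event, so in practice the table's steps concern Grade 3.

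**De-escalation.** Section 3.3 contains one trigger: "In the unexpected event that >1/6 patients in the first cohort experience a DLT, dose de-escalation will proceed by a 3 + 3 design". The target is 375 mg with 8 mg dexamethasone, then 125 mg steps of ONC201, with a floor of 125 mg and 8 mg.

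**The concern.** A site needs a single answer to what dose the first Phase 1 patient receives. The section that describes the scheme says 375 mg. The sections on administration and treatment say 625 mg and do not confine it to Phase 2 or to the upper cohort. In a 3+3 design every escalation decision depends on toxicities counted at a known dose level, so a wrong starting dose would remove the lower combination step that Section 3.3 plans.

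Table 6.1 has a related fault. It is written as if every patient were on 625 mg, although Section 3.3 assigns a whole cohort to 375 mg. For those patients the first step is above the assigned ONC201 dose and the second equals it.

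The de-escalation trigger is a smaller matter. It names the first cohort only and leaves the response to excess toxicity at 625 mg plus 20 mg to inference.

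**Working it through.** The plan states no figure on this point, so there is none to reproduce. The check compares the dose texts and then applies Table 6.1 to each relevant assigned dose.

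**Inputs.** Cohort doses 375 mg and 625 mg with dexamethasone 20 mg, and de-escalation pair 375 mg with 8 mg (Section 3.3); 625 mg (Sections 5.2 and 7.3); capsule strength 125 mg (Section 5.1.1); dosing on days 1, 8 and 15 of a 21-day cycle (Section 7.3); resume doses 500 mg + 8 mg and 375 mg + 8 mg (Table 6.1).

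**Step 1: can the starting-dose conflict be settled from the text?** The precedence rule in Section 7 puts the Schedule of Activities above the Section 7 text. The Schedule lists assessments and gives no ONC201 dose, so the rule has nothing to apply. It also does not reach Section 5.2.

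**Step 2: size of the starting-dose conflict.**

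- Capsules per dose: 625/125 = 5; 375/125 = 3.
- Ratio: 625/375 = 1.667, or +67% per dose.
- Per cycle: 3 × 625 = 1,875 mg against 3 × 375 = 1,125 mg, a difference of 750 mg.
- Patients concerned: the first cohort, 3 to 6 under 3+3.

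**Step 3: Table 6.1 against the assigned dose.** Change in ONC201 = (resume dose − assigned dose) / assigned dose. Change in dexamethasone = 8 mg − assigned dose.

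| Assigned ONC201 / dexamethasone | ONC201, first step (500 mg) | ONC201, second step (375 mg) | Dexamethasone, either step |
|---|---|---|---|
| 625 / 20 mg | −125/625 = −20% | −250/625 = −40% | −12 mg |
| 375 / 20 mg | +125/375 = +33% | 0/375 = 0% | −12 mg |
| 375 / 8 mg (only if de-escalation occurs) | +33% | 0% | 0 mg |

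Both steps lower ONC201 only from 625 mg. A 375/20 patient has dexamethasone alone reduced. A patient in an 8 mg de-escalation cohort has neither drug reduced.

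**Step 4: the trigger.** Within Section 3.3 the first cohort is 375/20, and the step to 375/8 lowers dexamethasone first. That is coherent. For excess toxicity at 625/20 no pair is written. The 3+3 design implies a return to 375/20, and Section 5.6 allows intermediate levels to be evaluated, so the fallback can be inferred but is not stated.

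**The case against.** The strongest reply is that the intended design can be recovered. Section 3.3 is the section devoted to the dosing scheme, and the synopsis sentence that assigns 625 mg also describes a 3+3 escalation up to that dose. This makes 375 mg the likely intention. It does not correct Sections 5.2 and 7.3, which a site will consult when dosing.

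On Table 6.1, Section 6 leaves modifications to clinical judgment, its footnote calls the steps reductions, and for other events or conflicting recommendations it prefers the adjustment that lowers the dose. So a real increase is unlikely, and that much stands. None of these clauses supplies a lower ONC201 dose for a patient on 375 mg.

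A reader might infer more than the documents support:

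- *That 625 mg is ordered for all patients.* Neither 5.2 nor 7.3 says so; they lack a qualifier.
- *That Section 3.1 adds a further contradiction.* Its plan to "explore the antitumor efficacy of orally administered ONC201 at 625 mg weekly in patients receiving concomitant dexamethasone" is a statement of aim and is compatible with a 375 mg lead-in.
- *That the first-cohort trigger does not work.* It works for 375/20. Leaving ONC201 unchanged at the first step is a design choice.
- *That a 375 mg patient has no usable step at all.* At 375/20, the second step is a real reduction of the combination through dexamethasone.
- *That very large increases are in prospect.* Larger percentages can be computed for 250 mg and 125 mg, but they need successive failed de-escalation cohorts and a literal reading that is itself unlikely.
- *That patients would receive an untested ONC201 dose.* Section 1.3 reports six single-agent patients who completed the 21-day window at 625 mg weekly. What would be lost is the lower step of the combination.

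**Conclusion.** The dose rules are internally inconsistent and wrong as written; the scheme in Section 3.3 is not itself in question. The main finding is the starting dose: 625 mg against 375 mg, +67% per dose and 750 mg per cycle, for a first cohort of 3 to 6 patients, if a site follows 5.2 or 7.3. Next is Table 6.1: taken literally it raises ONC201 by 33% for a 375 mg patient after a first Grade 3 event, and it never takes that patient below 375 mg. The unwritten fallback at 625/20 is minor.

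The direct exposure is Phase 1, up to 12 patients, plus Phase 2 if an ONC201 dose below 625 mg is selected. The synopsis wording for Phase 2 conflicts with Section 3.3 only if the selected ONC201 dose is not the anticipated 625 mg. Phase 2 power is unaffected, since the calculation in Section 8.2 rests on 30 patients and response rates of 10% and 30%, not on the dose. The conclusion assumes that 375 mg is the intended start, as Section 3.3 states. If 625 mg were intended, the inconsistency would remain and Section 3.3 would be the text to correct. It should be fixed.

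**What to change.** 1. In the synopsis and in Sections 5.2 and 7.3, replace the fixed 625 mg by the assigned cohort dose for Phase 1 and the RP2D for Phase 2.
2. Rewrite Table 6.1 as steps down from the assigned dose, with no step above it. One 125 mg capsule per step would keep 625 → 500 → 375 mg and give 375 → 250 → 125 mg, within the floor in Section 3.3. Add a rule for patients already at 125 mg ONC201 or 8 mg dexamethasone.
3. In Section 3.3, name the dose level to which the trigger applies and state the fallback ONC201 and dexamethasone pair for excess dose-limiting toxicities at 625/20. The clinical team should choose the pair.

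The cost is a wording amendment, with no added patients, visits or procedures.
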